## 2.3 Background and Justification

Atrial fibrillation is a debilitating disease with symptoms that reduce quality of life and put subjects at a higher risk of stroke than subjects with no atrial fibrillation. Current treatment options include antiarrhythmic drug therapy, catheter ablation for paroxysmal atrial fibrillation and concomitant surgical therapy. These treatment options have poor effectiveness outcomes and carry side effects from antiarrhythmic drugs and procedural risks from the surgical therapies. Currently catheter ablation is not indicated for the treatment of persistent and long standing persistent (herein referred to as persistent) atrial fibrillation and therefore subjects that have failed antiarrhythmic drug therapy and are not candidates or have failed surgical therapies have no other FDA approved treatment options.

Previous to this study, the tailored treatment for permanent atrial fibrillation (TTOP-AF) study was conducted to demonstrate the safety and effectiveness the Phased RF system. TTOP-AF was conducted between 2007 and 2010 and presented to the FDA Circulatory System Devices Panel on October 27, 2011. Based on the TTOP-AF data the panel voted that the Phased RF system was effective in the treatment of subjects with persistent atrial fibrillation. However, the panel was concerned with the peri-procedural stroke rate and pulmonary vein stenosis rates. Therefore the panel voted that the benefits of the Phased RF system did not outweigh the risks of treating subjects with persistent atrial fibrillation. Thus, Medtronic with the agreement of the FDA is conducting this study to demonstrate that the Phased RF system is safe after the implementation of mitigation strategies to lower the peri-procedural stroke rate (i.e. anticoagulation and catheter programming requirements). Therefore, the primary objective of the study is to confirm the safety of the Phased RF system and not to evaluate the system's effectiveness.

## 2.4 System Description

The Medtronic Phased RF System is intended to be used for mapping intracardiac electrograms and to deliver precise, temperature controlled radio frequency (RF) ablation therapy within the atria of the heart for the treatment of atrial fibrillation. The main components of the System are listed in Table 1.

Table 1: System Component Information

Component	Investigational or Market-released
Multi-Channel RF Ablation Generator	Investigational (US Only)
Catheter Interface Cable	Investigational (US Only)
Multi-Array Septal Catheter (MASC)	Investigational (US and Canada Only)
Multi-Array Ablation Catheter (MAAC)	Investigational (US and Canada Only)
Pulmonary Vein Ablation Catheter (PVAC)	Investigational (US Only)
Pulmonary Vein Ablation Catheter (PVAC GOLD)	Investigational (US and Canada** Only)
ECG Interface Box	Investigational (US Only)
ECG Interface Box Cable	Investigational (US Only)
ECG Amplifier Cable	Investigational (US Only)
GENius Jr. Remote Control	Investigational (US Only)
Remote Control Cable 15 or 25ft	Investigational (US Only)
Power Cord, North America	Investigational (US Only)

baseline information and relevant medical history will be summarized for all enrolled subjects, all subjects with a Phased RF ablation procedure (e.g. at least one Phased RF catheter placed in the left atrium), subjects randomized to the pulmonary vein stenosis (PVS) assessment cohort [REDACTED].

### **3.1.2 Summary of Ablation Procedures**

A summary of Phased RF ablation procedure information including procedure times, ablation locations, Phased RF ablation catheters used, and ablation energy modes will be summarized for procedures where at least one Phased RF ablation catheter was placed in the left atrium with Phased RF energy delivered.

### **3.1.3 Special Considerations**

#### **3.1.3.1 Missing Data**

In general, tipping point analysis methods will be utilized to evaluate the impact of missing data. The analysis details will be specified for individual objectives in the following section.

#### **3.1.3.2 Randomization**

Upon confirmation that all inclusion and no exclusion criteria have been met, the Patient Informed Consent form has been signed, and baseline testing has been completed, a subject (except the first enrolled subject at a study center) may be randomized to either [REDACTED] the PVS assessment cohort, or to the no additional testing cohort. The first enrolled subject at each study center is automatically assigned to the no additional testing cohort.

Specifically, 100 subjects will be randomly selected from the first 200 enrolled subjects to participate in the PVS assessment cohort. The randomization schedule will not allow the first enrolled subject at a study center to be selected into the PVS assessment cohort.

[REDACTED]

The remaining subjects will be assigned to the no additional testing cohort.

To implement the requirements above, the randomization will be centralized and not stratified by study center. A Medtronic statistician will create the randomization schedule.

[REDACTED]

#### **3.1.3.3 PVAC and PVAC GOLD catheter use**

If Phased RF ablation procedures are performed with more than one PVAC model, subgroup analyses may be performed on the primary and secondary objectives as well [REDACTED] by PVAC model. Specifically, should the need for a subgroup analysis occur, three subgroups will be defined as subjects ablated with only the PVAC catheter (index and reablation procedure), subjects ablated with only the PVAC GOLD catheter (index and reablation procedure), and subjects ablated with both

the PVAC and PVAC GOLD catheter (e.g. index procedure with PVAC catheter and reablation procedure with PVAC GOLD catheter). For each of these objectives, Fisher's Exact test would then be used to assess the heterogeneity of the results by PVAC catheter subgroup should the need for a subgroup analysis arise.

### 3.1.4 Reports for Which This Statistical Analysis Plan Applies

#### 3.1.4.1 PMA Report

This SAP applies to the PMA report for the VICTORY AF study. The visit cutoff date will be the day on which 300 ablated subjects have completed the 30 day post reablation procedure visit or have had the opportunity for a reablation visit (between 0 and 6 months after the index procedure) meaning the subject has completed the 6-month post-index ablation visit or exited the study prior to a reablation procedure.

Alternatively, the study may stop early for futility prior to completing enrollment if more than 6 procedure and/or device related strokes occur within the 30 day peri-procedural period.

#### 3.1.4.2 Final Report

This SAP applies to the final report for the VICTORY AF study which will take place once all enrolled subjects have had the opportunity to have a 6 month visit following their final procedure, or official study closure defined as when Medtronic and/or regulatory requirements have been satisfied per the Clinical Investigational Plan (CIP), whichever occurs first. There will be no visit cut-off date for the final report. Instead, all the available data at the time of data freeze will be included in the final report.

## 3.2 Primary Objective: 30-day Procedure and/or Device Related Stroke Rate

Demonstrate that the observed incidence of procedure and/or device related incidence of new stroke (excludes transient ischemic attack) within 30 days of an ablation procedure (index or reablation) with the Phased RF System is less than 1.8% with observed upper confidence boundary that is less than 3.5%.

### 3.2.1 Hypothesis

To pass the primary objective the following two conditions must be met:

1. The observed procedure and/or device related stroke rate must be less than 1.8%.
2. The exact one-sided upper 95% confidence interval for the procedure and/or device related stroke rate must be less than 3.5%.

The formal statistical hypothesis for the primary objective is:

$$H_0: \pi \geq 3.5\%$$

$$H_a: \pi < 3.5\%$$

where  $\pi$  is the true 30-day post ablation procedure (index or reablation) procedure and/or device related stroke rate.

### 3.2.2 Definition of Procedure and/or Device Related Stroke

Procedure and/or device related strokes are defined as events classified by the Clinical Events Committee (CEC) meeting all of the requirements in Table 5 in the VICTORY AF CIP (version 5). Specifically, the stroke must have a symptom onset date within 30 days of an ablation procedure where at least one phased RF catheter is deployed into the left atrium (i.e. placed in the left atrium with Phased RF energy delivered) and be considered related to the procedure and/or device by the CEC.

Specifically, in the Medtronic use only CRF (MDT ADVERSE EVENT), the following fields must be checked in relation to the CEC determination:

- Adverse Event is denoted neurological related with a diagnosis of “stroke”
- Adverse Event is denoted as Related to the Phased RF study procedure and/or related to one or more of the following system components: PVAC, PVAC GOLD, MAAC, MASC, or Medtronic GENius™ Multi-Channel RF Generator
- Adverse Event is denoted as “Yes” for meeting the periprocedural definition

Additionally, the following values are required on the relevant procedure CRF (treatment or reablation) to meet the primary endpoint:

- Time of initial Phased RF Catheter deployment in left atrium must be non-missing
- At least one record of Phased RF energy delivery must be present in the PVAC/PVAC GOLD, MAAC, and/or MASC ablation log CRF forms
- Non-investigation catheter use in the left atrium must NOT be checked
- The onset date of the stroke must be no more than 30 days following the index procedure (if stroke occurs prior to any reablation procedure) or no more than 30 days following a reablation procedure if stroke occurs following a reablation procedure.

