6.2 Study objectives

6.2.1 Primary safety objective

Demonstrate that the observed incidence of procedure and/or device related incidence of new stroke (excludes transient ischemic attack) within 30 days of an ablation procedure (index or reablation) with the Phased RF System is less than 1.8% with observed upper confidence boundary that is less than 3.5%.

The definition of stroke is provided in the Table below. To meet the primary endpoint an event must meet all of the criteria in Table 5 below as determined by the clinical events committee (CEC).

Table 5: Protocol defined stroke

Definition	Hemorrhagic and Ischemic stroke with rapid onset of a focal or global neurological deficit or other neurological signs/symptoms consistent with stroke
Symptom duration	Duration of focal or global neurological deficit ≥ 24 hours; OR Duration of focal or global neurological deficit < 24 hours IF : 
 • Therapeutic interventions 
 ○ Thrombolytic therapy ○ Intracranial angioplasty OR • Neuroimaging documents a new hemorrhage or ischemic infarct OR • Neurological deficit results in death
Periprocedural definition	Within 30 days of Phased RF ablation procedure where the investigational catheter was placed in the left atrium
Diagnosis	Appropriate diagnostics will be determined by the site's neurologist's clinical evaluation and include one or more of the following: 
 • Clinical signs and symptoms consistent with focal or global neurologic deficit • Neuroimaging procedure (CT or MR scan or cerebral angiography) • Lumbar puncture (i.e. subarachnoid hemorrhage) AND Adjudicated as peri-procedural stroke by clinical events committee

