11. RISK ANALYSIS

The residual risks associated with the Phased RF System have been found to be acceptable and have been mitigated to the fullest extent possible. The potential benefits related to the use of the Phased RF System have been determined to outweigh any potential risks.

For geographies where the study devices are market-approved, there are no known incremental risks to the study subject as a result of participating in the study. These risks are documented in the product labeling. However, there are potential risks and side effects associated with an ablation and required study follow-up procedures (e.g. CT and/or MRI scans for [REDACTED] PV stenosis [REDACTED]). These risks are provided in the Informed Consent Form.

Table 14 describes the potential risks that have been identified since the TTOP-AF study and the mitigations that have been put in place to minimize the risks.

Table 14: Potential Risks and Risk Minimization

Potential Risks	Risk Minimization
Peri-procedural stroke	
Based on literature review (provided Executive Summary and Report of Prior Investigations), the continuance of oral anticoagulation prior, during and post ablation procedure reduces the risks of stroke without increasing the risk of bleeding complications, particularly with therapeutic INR (2.0-3.5).
 
Maintaining procedural ACT >350 has also been associated with reduced stroke incidence.
 
Rigorous sheath management during catheter introduction and exchanges has demonstrated a reduced likelihood of air egress during the ablation procedure.

Potential Risks	Risk Minimization

[REDACTED]
	
[REDACTED]

Pulmonary vein stenosis
	
Physician operators will be trained on visualization techniques (e.g. fluoroscopy imaging in LAO and RAO views depending on pulmonary vein target) to verify the PVAC or PVAC GOLD catheter is not situated within the tubular portion of the PV prior to ablation.

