12.2.3 Definition of procedure and/or device related stroke

Procedure and/or device related strokes are defined as events classified by the CEC meeting all of the requirements in Table 5. Specifically, the stroke must have a symptom onset date within 30 days of an ablation procedure where at least one phased RF catheter is deployed into the left atrium and be considered related to the procedure and/or device by the CEC.

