12.2.5 Experimental design and analysis methods

This study is a prospective, unblinded, multi-center, worldwide clinical study designed to evaluate the procedure and/or device related peri-procedural stroke rate within 30 days of an ablation procedure with the Phased RF System. The study will be considered successful if the primary objective is met. A single decision regarding study success will be made once all subjects with a Phased RF ablation procedure have had the opportunity for a reablation procedure (completed the 6-month visit) or completed the 30-day post-reablation visit if a reablation is required. Alternatively, the study may stop early for futility if more than six (6) procedure and/or device related peri-procedural strokes occur prior to completing enrollment.

For computing the peri-procedural stroke rate, the denominator will be all subjects with at least one ablation procedure attempt where at least one of the Phased RF catheters was deployed into the left atrium and have at least 30 days of post-

procedure follow-up. Also, subjects who have a procedure and/or device related peri-procedural stroke as classified by the CEC with symptom onset date within 30 days of a Phased RF ablation procedure will be included. The numerator for the stroke rate will be all subjects included in the denominator that had a procedure and/or device related stroke as classified by the CEC with a symptom onset date within 30 days of a Phased RF ablation procedure. The null hypothesis will be rejected in favor of the alternative if the observed stroke rate is less than 1.8% and the exact one-sided upper 95% confidence interval is less than 3.5%.

Additionally, a one-sided exact p-value will be computed for comparing the observed stroke rate to the performance goal of 3.5%.

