12.2.7 Determination of subjects for analysis

All subjects with at least one attempted ablation procedure with the Phased RF system where at least one investigational catheter was deployed into the left atrium and have completed at least 30 days of post-procedure follow-up will be included in the analysis. Additionally, all subjects with a procedure and/or device related stroke as classified by the CEC with a symptom onset date within 30 days of a procedure where a Phased RF catheter was placed in the left atrium will be included in the analysis regardless of whether the subject has less than 30 days of post-procedural follow-up.

In the rare instance where a subject has a non-investigational ablation catheter placed in the left atrium, the subject will be excluded from the analysis of the primary objective. However, a summary of all peri-procedural AEs will be provided for any subject excluded from the primary analysis.

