### 3.2.5 Determination of Subjects for Analysis

All subjects with at least one attempted ablation procedure with the Phased RF system where at least one investigational catheter was deployed into the left atrium (i.e. placed in the left atrium with Phased RF energy delivered) and have completed at least 30 days of post-procedure follow-up will be included in the analysis. Additionally, all subjects with a procedure and/or device related stroke as classified by the CEC with a symptom onset date within 30 days of a procedure where a Phased RF catheter was deployed in the left atrium will be included in the analysis regardless of whether the subject has less than 30 days of post-procedural follow-up.

In the rare instance where a subject has a non-investigational ablation catheter placed in the left atrium, the subject will be excluded from the analysis of the primary objective. However, a summary of all peri-procedural adverse events (AEs) will be provided for any subject excluded from the primary analysis.

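### The SAP counts a stroke only if RF energy was delivered, whereas the protocol's Table 5 counts it once the catheter is placed in the left atrium

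*SAP*

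**What the plan says.** **Protocol.** Table 5 (section 6.2.1) sets the periprocedural criterion as "Within 30 days of Phased RF ablation procedure where the investigational catheter was placed in the left atrium". Section 12.2.7 keeps a subject with a qualifying stroke on the same basis, even with short follow-up: "within 30 days of a procedure where a Phased RF catheter was placed in the left atrium will be included in the analysis". Section 12.2.3 uses *deployed* without an energy condition ("within 30 days of an ablation procedure where at least one phased RF catheter is deployed into the left atrium"), and so does the denominator in section 12.2.5: "at least one ablation procedure attempt where at least one of the Phased RF catheters was deployed into the left atrium". Section 12.1.1 describes a Phased RF ablation procedure as one with at least one catheter placed in the left atrium. None of the protocol's primary-endpoint text asks for energy delivery.

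**SAP.** Section 3.2.2 refers to Table 5 of CIP version 5 and then requires that "at least one phased RF catheter is deployed into the left atrium (i.e. placed in the left atrium with Phased RF energy delivered". Its list of CRF fields asks for a non-missing time of catheter deployment and, as a separate item, at least one energy record in an ablation log. Section 3.2.5 defines the analysis set by "at least one investigational catheter was deployed into the left atrium (i.e. placed in the left atrium with Phased RF energy delivered". Item 1 of the denominator in section 3.2.3 has the same energy condition. Item 2, which admits CEC-classified stroke subjects whatever their follow-up, does not repeat it.

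**The concern.** Consider a procedure stopped after a Phased RF catheter has entered the left atrium but before any energy, with complete data. If the subject then has a stroke that the CEC judges related, Table 5 counts it and SAP 3.2.2 does not.

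The primary endpoint is safety, and the exposure of interest includes catheter introduction. The protocol's own risk table (Table 14) lists handling at that step among the stroke mitigations: "Rigorous sheath management during catheter introduction and exchanges has demonstrated a reduced likelihood of air egress during the ablation procedure". Introduction comes before energy, so a stroke arising there could itself be the reason that no energy was delivered. Conditioning on energy delivery then selects subjects on a post-exposure event that the outcome can influence.

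There is also an internal mismatch. Protocol section 10 ties the early-futility count to strokes meeting Table 5. The same stroke could count toward futility and be absent from the success analysis.

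**Working it through.** **1. Reproduce the plan's figures.** Inputs (SAP 3.2.4, Protocol 12.2.6): N = 300, one-sided alpha 0.05, performance goal 3.5%, observed rate below 1.8%. The exact one-sided 95% upper bound for x strokes in n subjects is the 0.95 quantile of Beta(x + 1, n − x).

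- 5/300 = 1.67%, upper bound 3.47%: passes.
- 6/300 = 2.00%, upper bound 3.91%: fails.

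The pass limit is therefore 5. P(X ≤ 5) for X ~ Bin(300, p) is 91.7% at p = 1%, 80.2% at 1.3%, 54.6% at 1.8% and 4.76% at 3.5%. This agrees with the stated 90%, 80%, 55% and type I error below 5%. The power figures are not in question.

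**2. Follow one stroke after a no-energy procedure through each text.**

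| Situation | Table 5 and Protocol 12.2.7 | SAP 3.2.2, 3.2.3 item 1, 3.2.5 |
|---|---|---|
| Only Phased RF procedure, no energy | Stroke and subject counted | Stroke not counted; subject out of the denominator |
| Energy delivered at another procedure, with 30 days of follow-up | Stroke and subject counted | Stroke not counted; subject kept as stroke-free |
| No-energy procedure, no stroke, 30 days of follow-up | Subject counted if *deployed* means placed | Subject out of the denominator |

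**3. Effect of one such stroke at the boundary.**

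- Starting from 6/300 under Table 5 (fails), the SAP removes the stroke and the subject: 5/299 = 1.67%, upper bound 3.48%, passes.
- Starting from 5/300 under the SAP (passes), Table 5 adds both back: 6/301 = 1.99%, upper bound 3.90%, fails.
- Six strokes pass only from N = 336. Full enrolment with the protocol's 26% pre-procedure attrition gives 420 × 0.74 ≈ 311 index procedures.

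**4. Effect in the other direction.** Dropping stroke-free no-energy subjects shrinks the denominator. With 5 strokes, 300 subjects pass (3.47%), while 297 give 1.68% with an upper bound of 3.51% and fail. Both examples in this step and the 5/299 in step 3 assume that N is not topped up to 300.

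**5. How likely is a reversal?** The documents give no rate of no-energy procedures. Assume 1% to 2%, so 311 × 0.01 to 311 × 0.02 is about 3 to 6 subjects. Assume also the plan's 1.3% stroke rate in everyone.

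- P(exactly 5 strokes among 300 energy-delivered subjects) = 0.153.
- P(at least one stroke among 3 others) = 1 − 0.987³ = 0.038; among 6 others, 1 − 0.987⁶ = 0.075.
- The product is about 0.6% to 1.2%.

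**6. Effect on type I error.** Let q be the assumed share of Table 5 strokes that follow no-energy procedures. With a true Table 5 rate of 3.5% and N held at 300, the chance of passing under the SAP count is P(X ≤ 5) at p = 3.5% × (1 − q):

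| q | Chance of passing |
|---|---|
| 0 | 4.76% |
| 1% | 5.07% |
| 2% | 5.39% |
| 5% | 6.5% |
| 10% | 8.7% |
| 20% | 15.4% |

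No document says where q lies. The larger values need no-energy procedures to carry a clearly higher stroke risk or to be more common than assumed in step 5.

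**The case against.** **The energy wording is a deliberate clarification.** The SAP change history presents it as explaining *deployed*, a word the protocol also uses in 12.2.3, 12.2.5, the first sentence of 12.2.7 and Table 10. This has weight where the protocol says *deployed*. It cannot explain Table 5 or the second sentence of 12.2.7, which say *placed*.

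**The versions differ.** The SAP cites CIP version 5 and plans 350 subjects at about 40 centers. The supplied protocol plans up to 420 at up to 55 and appears to be a different version. A reader might infer that the SAP contradicts the version it cites. That cannot be shown, because the Table 5 of version 5 is not available. What can be shown is that the two supplied texts conflict.

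**Item 2 of SAP 3.2.3 may readmit the stroke subject.** It carries no energy wording. However, its term for the stroke is defined in 3.2.2 with energy, and 3.2.5 readmits only after a catheter was *deployed*, which the same section defines with energy. At best the SAP is ambiguous.

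**The stroke would not be hidden.** The CEC reviews every adverse event against Table 5, and both documents promise a summary of peri-procedural events, which may cover this exclusion. This stands as far as disclosure goes, but neither route puts the stroke into the success rule.

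**The mechanism is partly conjecture.** Table 14 speaks of introduction and exchanges, and exchanges can follow energy. The protocol recommends the discharge neurological evaluation after anesthesia has worn off, so a stroke recognised in time to stop the case is not the obvious path. This limits how often the problem would arise.

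**Conclusion.** The conflict between the supplied documents is real and concerns the primary endpoint. Under SAP 3.2.2 a CEC-related stroke tied to a procedure with catheter placement but no energy is not a primary event, although Table 5 counts it.

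Two stronger readings do not hold. A reader might infer that the subject always leaves the analysis together with the stroke. SAP 3.2.3 item 1 needs only one procedure with energy and 30 days of follow-up, so a subject treated at the index procedure stays in the denominator after a no-energy reablation, as stroke-free. A reader might also infer that the rule can only favour passing. Losing strokes does favour passing, but dropping stroke-free no-energy subjects works slightly against it.

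One stroke can reverse the trial result, but only at a boundary count. Under the assumed 1% to 2% of procedures and a uniform 1.3% stroke rate, the chance is about 0.6% to 1.2%. It would be higher if no-energy procedures carried more stroke risk, which no document quantifies. The case for correction rests mainly on the principle that a safety endpoint should not depend on a post-exposure event that the outcome may prevent.

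**What to change.** In SAP 3.2.2, 3.2.3 and 3.2.5, define the qualifying procedure and the primary safety population as Table 5 does: a Phased RF catheter placed in the left atrium, whether or not energy was delivered. Remove the mandatory energy-record item from the CRF list in 3.2.2, and make item 2 of 3.2.3 use the same definition. Report the stroke rate among energy-delivered subjects as a sensitivity analysis. Confirm that the CIP version cited in the SAP is the one in force. Definitions for the other objectives are outside this change.

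The cost is a SAP wording revision before data are analysed. SAP 3.2.2 already lists catheter deployment time and energy records as separate CRF items, and CEC adjudication against Table 5 is already planned. The downside is that a few partially exposed subjects enter the denominator; the sensitivity analysis shows their effect.

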### 3.2.3 Experimental Design and Analysis Methods

This study is a prospective, unblinded, multi-center, worldwide clinical study designed to evaluate the procedure and/or device related peri-procedural stroke rate within 30 days of an ablation procedure with the Phased RF System. The study will be considered successful if the primary objective is met. A single decision regarding study success will be made once all subjects with a Phased RF ablation procedure have had the opportunity for a reablation procedure (completed the 6-month visit) or completed the 30-day post-reablation visit if a reablation is required. Alternatively, the study may stop early for futility if more than six (6) procedure and/or device related peri-procedural strokes occur prior to completing enrollment.

For computing the peri-procedural stroke rate, the denominator will include:

1. All subjects with at least one ablation procedure attempt where at least one of the Phased RF catheters was deployed into the left atrium with Phased RF energy delivered and have at least 30 days of post-procedural follow-up, AND
2. Subjects with a procedure and/or device related peri-procedural stroke as classified by the CEC within 30-days of a Phased RF procedure regardless of the subject’s follow-up duration.

The numerator for the stroke rate will be all subjects included in the denominator that had a procedure and/or device related stroke as classified by the CEC with a symptom onset date within 30 days of a Phased RF ablation procedure. The null hypothesis will be rejected in favor of the alternative if the observed stroke rate is less than 1.8% and the exact one-sided upper 95% confidence interval is less than 3.5%.

Additionally, a one-sided exact p-value will be computed for comparing the observed stroke rate to the performance goal of 3.5%.

[REDACTED]

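### SAP 3.2.2 puts a catheter condition on the endpoint stroke that is worded more broadly than the subject exclusion in SAP 3.2.5, so a CEC-adjudicated related stroke could be dropped while its subject stays in the denominator

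*SAP*

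**What the plan says.** The event and the analysis set are defined in several places, and the catheter conditions differ.

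- **Event, protocol.** Protocol 12.2.3 states: "Procedure and/or device related strokes are defined as events classified by the CEC meeting all of the requirements in Table 5". It adds onset within 30 days of a procedure with a Phased RF catheter in the left atrium, and CEC-judged relatedness. It does not mention other catheters.
- **Event, SAP.** SAP 3.2.2 repeats this, lists the CEC fields that must be set, and then adds that "the following values are required on the relevant procedure CRF (treatment or reablation) to meet the primary endpoint". One of those values is "Non-investigation catheter use in the left atrium must NOT be checked". The bullet is not limited to ablation catheters.
- **Denominator and numerator.** SAP 3.2.3 item 1 takes subjects with Phased RF energy delivered in the left atrium and at least 30 days of follow-up. Item 2 adds "Subjects with a procedure and/or device related peri-procedural stroke as classified by the CEC within 30-days of a Phased RF procedure", whatever the length of follow-up. The numerator is those in the denominator with a related stroke as classified by the CEC and onset within 30 days. The CRF catheter check is not restated.
- **Exclusion.** SAP 3.2.5 removes a subject only where "a subject has a non-investigational ablation catheter placed in the left atrium, the subject will be excluded from the analysis of the primary objective". Protocol 12.2.7 has the same limit: "a non-investigational ablation catheter placed in the left atrium, the subject will be excluded from the analysis of the primary objective".

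**The concern.** Where a non-study ablation catheter was used, the exclusion takes the subject out of numerator and denominator alike. Both documents say so and agree. The 3.2.2 bullet works differently. It acts on the stroke alone, and its wording reaches beyond the catheters that trigger the exclusion. A subject whose box was checked for something other than an ablation catheter would not be excluded, yet the stroke would fail the endpoint definition.

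This affects the only pass/fail test in the study, and it can act in one direction only: the bullet can remove strokes and can never add one. The safeguard in SAP 3.2.5, a summary of peri-procedural adverse events for subjects excluded from the primary analysis, would not cover such a subject, because a subject retained as a non-event has not been excluded.

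**Working it through.** **1. The plan's own figures.** Inputs from SAP 3.2.4 and Protocol 12.2.6: n = 300, one-sided alpha 0.05, performance goal 3.5%, observed rate below 1.8%, assumed true rate 1.3%.

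The study passes with x strokes if x/n < 0.018 and U(x, n) < 0.035, where U is the exact one-sided 95% upper bound, the 0.95 quantile of Beta(x + 1, n − x).

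- x = 5: 5/300 = 1.67%, U = 3.47%, pass.
- x = 6: 6/300 = 2.00%, U = 3.91%, fail.

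The pass limit is therefore 5, and power is P(X ≤ 5) for a binomial count with n = 300:

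| True rate | Computed P(X ≤ 5) | Stated |
|---|---|---|
| 1.0% | 91.7% | 90% |
| 1.3% | 80.2% | 80% |
| 1.8% | 54.6% | 55% |
| 3.5% | 4.76% | below 5% |

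The stated figures are reproduced to within 2 percentage points.

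**2. One subject traced through the rules.** Suppose Phased RF energy was delivered, the CRF box is checked, and the CEC adjudicates a related stroke within 30 days. Suppose this is the sixth such stroke among 300 subjects.

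| Reading | Subject | Stroke | Result |
|---|---|---|---|
| A. Box checked for a non-ablation catheter; 3.2.2 governs; at least 30 days of follow-up | kept by 3.2.3 item 1 | not counted | 5/300 = 1.67%, U = 3.47%, pass |
| B. As A, but under 30 days of follow-up, and 3.2.2 also governs item 2 | dropped | not counted | 5/299 = 1.67%, U = 3.48%, pass |
| C. Box checked for a non-ablation catheter; numerator follows CEC classification alone, as 3.2.3 reads | kept | counted | 6/300 = 2.00%, U = 3.91%, fail |
| D. Box records ablation catheters only | excluded by 3.2.5 | excluded with the subject | 5/299 = 1.67%, U = 3.48%, pass |

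Reading D is the exclusion that both documents intend, and under it the two rules do not conflict. Readings A, B and C come from the same record and the same SAP. They differ only in which section governs and in length of follow-up.

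Comparing A with B shows that keeping the subject in the denominator hardly matters numerically (3.47% against 3.48%). The effect comes from losing the event.

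**3. Illustration only.** The documents give no frequency. Assume that a share q of related strokes is lost in this way. The chance of passing at a true rate of 3.5% is then P(X ≤ 5) with n = 300 and rate 0.035 × (1 − q):

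| Assumed q | Rate used | Chance of passing |
|---|---|---|
| 0 | 3.500% | 4.8% |
| 5% | 3.325% | 6.5% |
| 10% | 3.150% | 8.8% |
| 20% | 2.800% | 15.4% |

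Nothing in the documents supports any particular q above zero.

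**The case against.** The best defence is that the bullet is CRF shorthand for the 3.2.5 exclusion. The procedure-CRF bullets in 3.2.2 run parallel to 3.2.5: catheter in the left atrium, energy delivered, no outside catheter, onset within 30 days. Elsewhere the documents write plain catheter where an ablation catheter is meant. The study system is itself intended for mapping, the procedure steps in Protocol 7.9 map with it, and the additional components in Protocol 4.1 are return electrodes, sheaths, dilators and needles. No section mentions an outside mapping or diagnostic catheter in the left atrium. This stands as far as it goes: reading D is plausible and cannot be ruled out without the CRF. It cannot be confirmed either, and if it is correct, adding the word ablation changes nothing.

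A second defence is that the stroke would be counted anyway. The 3.2.3 numerator goes by CEC classification, and Protocol 10.3 says that the CEC's determination is the one used in analysis. This also stands in part. It shows that the SAP conflicts with itself; it does not show that the event is safe, because 3.2.2 calls its CRF values required. Text after the numerator rule in 3.2.3 is redacted, so the implementation cannot be checked.

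A reader might infer that the SAP voids the stroke whenever any outside catheter was used, so that a subject with a mapping catheter is scored stroke-free. The documents do not support that. The scope of the box is unknown, no such catheter use is described, 3.2.3 points the other way, and a subject with under 30 days of follow-up could leave both counts. Nor can item 2 be used to keep the subject while 3.2.2 is used to discard the stroke. Item 2 and the numerator use the same CEC-based term, and it must carry one meaning in both.

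**Conclusion.** The mismatch in wording is certain. SAP 3.2.2 sets a broader catheter condition on the stroke than SAP 3.2.5 and Protocol 12.2.7 set on the subject, and neither Protocol 12.2.3 nor the SAP 3.2.3 numerator contains that condition. Whether it ever costs an event depends on two things the documents leave open: whether the CRF box can be checked for a non-ablation catheter, and whether 3.2.2 or 3.2.3 governs the count.

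If both go the wrong way, a CEC-adjudicated related stroke is lost, and at n = 300 one such loss is enough to turn 6 strokes into 5 and a fail into a pass. A reader might take the 15.4% in the illustration as the study's true type I error. It is not, because every q above zero is an assumption. The plan's stated power and type I error are not wrong. The point deserves correction because the condition can only favour passing a safety endpoint whose limit is five events, and because two programmers could follow the SAP faithfully and report different primary results.

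**What to change.** Do one of the following in SAP 3.2.2:

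- limit the bullet to non-investigational ablation catheter use in the left atrium, in the same terms as 3.2.5; or
- delete the bullet and let 3.2.5 alone decide which subjects leave the analysis.

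Under either option, every CEC-adjudicated related stroke in an analysed subject should count, and 3.2.2 and 3.2.3 should say so consistently. The SAP should also state what the CRF field records, since the 3.2.5 exclusion presumably relies on it too. A sensitivity analysis counting every CEC-adjudicated related stroke would be a reasonable addition but is not essential once the wording agrees.

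The cost is one line of SAP text, the matching line of program code and a sentence defining the field. Sample size, power and the success criterion are unaffected. If the box does not separate ablation catheters from others, the catheter type would have to come from another source in the procedure record; the documents do not show whether the procedure form holds it.
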